10.3. Statistical Analyses

10.3.1. Pharmacodynamic Analyses

Endpoint	Statistical Analysis Methods
Primary	
The association of Ang II with RV function (measured by PASP and RV size ratio) will be modelled using a Bayesian repeated measures mixed effects linear regression model, where PASP and RV size ratio are joint response variables, and including subject as a random effect and log(Ang II), age and sex as fixed effects. The model will be used to make a probabilistic prediction of PASP and RV size ratio for two reference values of Ang II, and hence an estimate for the probability of RV dysfunction (defined as PASP > 40 mmHg or RV size ratio > 0.6, following Boissier 2013) for the two given Ang II levels will be obtained using mean values for the other continuous covariates and averaging over all levels of class effects for categorical covariates.
 
The above modelling may use a modified Ang II value (modification based on the corresponding Ang(1-7) result to account for potential inhibitory interactions); details to be provided in the reporting and analysis plan (RAP).
 
The primary analysis will use the Evaluable population.

Secondary	
Association of Ang(1-7) with RV function (measured by PASP and RV size ratio) and of Ang II/Ang(1-7) with RV function (measured by PASP and RV size ratio) will both be modelled as per the primary analysis described above. These analyses will be done using the Evaluable population.
 
A model including both Ang II and Ang(1-7) as co-predictors of RV function may also be built, to explore the relationship between RV function and the envisaged dual action of angiotensin converting enzyme (ACE)2 effecting a reduction in Ang II together with a simultaneous increase in Ang(1-7).
 
Incidence of PCD and ACP during the three days of the study period and prevalence of pre-existing PCD/ ACP on entry to the study will be reported with 95% confidence intervals. This analysis will be done using the Completed population (which includes a clause to include participants who have an onset of PCD/ ACP but are subsequently withdrawn from the study before all three days' worth of data are collected without withdrawing consent).
 
The distribution of PASP, RV size ratio and other measurements of RV function in mechanically ventilated participants will be assessed via a combination of descriptive summary tables and outputs from the statistical modelling.

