2. SUMMARY OF KEY PROTOCOL INFORMATION

2.1. Changes to the Protocol Defined Statistical Analysis Plan

Except for the planned modelling of the Ang II / Ang(1-7) ratio there were no changes or deviations to the originally planned statistical analysis specified in the protocol amendment 3 (27-FEB-2019).

The protocol originally stated that the ratio of Ang II / Ang(1-7) would be derived for each participant and formally modelled using the same approach as the primary endpoint. However, the statistical model fitting will not take place. Modelling the ratio does not adequately represent aspects of the underlying biology. For example if a participants Ang II and Ang(1-7) values were both 10 pg/mL and another's were both 10000 pg/mL their derived ratios would be identical (one). Modelling a simple ratio naïvely implies the same significance and biological effect for each participant, even though they are at completely different places on the underlying concentration response curves. The additional approach to jointly analyzing Ang II and Ang (1-7) described in the protocol (and in Section 7.2.5.1) will now be the sole approach to modelling Ang II / Ang(1-7) ratios.

Note: The simple summary statistics for the Ang II / Ang(1-7) ratios will still be produced because they capture information about enzyme activity.

Protocol amendment #3 (27-FEB-2019) increases the duration that a participant may be mechanically ventilated, before they are included in the study – from \leq 24 hours to \leq 48 hours. This change has been made to assist enrolment of participants into the study, but the sponsor considers that it will not impact the objectives of the study. Informal checks may be made by the study statistician to confirm this assumption (e.g. visual comparisons

of results grouped by protocol version enrolled under). Any such checks would not be formally documented/reported unless a difference was apparent in which case the likely approach would be to perform additional sensitivity analyses with appropriate adjustments to the original output(s) to account for the protocol version.

At the time of writing the Critical Components RAP recruitment was going to commence under Protocol Amendment #1 and switch to amendment #2 as soon as possible. The initial set of subjects enrolled under amendment #1 have a reduced number of endpoints available because amendment #2 added the following endpoints:

CRF form	Questions / Endpoint

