2.4. Statistical Hypotheses / Statistical Analyses

This study is designed to test the hypothesis that an association exists between RAS peptides, primarily plasma Ang II and Ang(1-7) levels, and RV function in mechanically ventilated patients. No formal statistical hypotheses are being tested in this exploratory study.

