7.2.5. Statistical Analyses / Methods

The secondary statistical analyses are divided into three subcategories, with the first being variations on the primary analysis: analyses following the same form as the primary analysis but using a different RAS peptide measurement in place of Ang II.

The second subcategory models the joint association of Ang II and Ang(1-7) on RV function (Note: if the observed data ranges do not permit parameter estimation/model convergence of the proposed model then simpler alternative models may not be attempted; but if they are any methodology would be described in the CSR).

The third subcategory of the secondary analyses is an estimate of disease incidence within the mechanically ventilated population.

Details of the planned displays are provided in [Appendix 10](#): List of Data Displays and will be based on GSK data standards and statistical principles.

Unless otherwise specified, endpoints / variables defined in Section [7.2.1](#) will be summarised using descriptive statistics, graphically presented (where appropriate) and listed.

7.2.5.1. Supportive Models to the Primary analysis, using other RAS peptides in place of Ang II

Supportive models to the primary analysis will be conducted following the same methodology as the primary analysis models (see Section [7.1](#)) but with changes as described below.

The first supportive model will include Ang(1-7) as a time-point-level covariate instead of Ang II, and the corresponding reference value from Section [7.1.5](#).

Note: An optional supportive model would include Ang(1-5) as a time-point-level covariate instead of Ang II, and the corresponding reference value from Section [7.1.5](#). This model may be attempted if the Ang II and Ang(1-7) modelling does not produce a clear/consistent outcome and/or the observed level of correlation between Ang(1-5) and Ang(1-7) data is deemed likely to result in a different conclusion (*a priori* expectation Ang(1-7) and Ang(1-5) data will be highly correlated, and so any modelling would be expected to produce similar conclusions and duplication would not add value).

7.2.5.2. Combined model of the joint association of Ang II and Ang (1-7) with RV function

Endpoint / Variables

 PASP and RV Size Ratio on Day 1, Day 2 and Day 3 where available Time matched concentration of Ang II (Denoted as A in model specification) Time matched concentration of Ang (1-7) (Denoted as B in model specification)

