Model Specification
The relationship between Ang II and Ang(1-7) (as joint explanatory variables) and the

joint bivariate distribution of PASP and RV size ratio (the outcome variables) will be analysed using a Bayesian multivariate non-linear regression model.

For simplicity, the repeated measures aspect of the data structure is not being modelled by first intent and Hill coefficients are assumed to be 1. If data permit, a similar strategy to the primary analysis that accounts for repeated measures may be attempted (e.g. Kronecker product with an AR(1) structure for Tigma), but only the model used for final inference would be reported. If data do not permit the planned model to be fitted no further modelling is proposed. However, if alternative model(s) are attempted and successful, they would be described in the CSR).

The multivariate normal model is specified as follows (for maximum flexibility time has been left in the parameter definitions) :

$$\begin{pmatrix} y_{it1} \\ y_{it2} \end{pmatrix} \sim MVNormal \left(\begin{pmatrix} \mu_{it1} \\ \mu_{it2} \end{pmatrix}, \Sigma \right)$$

where y_{itj} represents the observed value for the i th participant, the t th time-point and the j th outcome (i.e. $j = 1$ representing PASP and $j = 2$ representing RV size ratio), μ_{itj} represents the expected value for the i th participant, t th time-point ($t = 1, 2, 3$) and the j th outcome ($j=1$ and $j=2$ as above), and Σ represents a variance-covariance (vcov) matrix for the two outcome variables.

The expected values, μ_{itj} , are modelled as follows:

$$\mu_{itj} = \frac{Basal_j + Max_{Bj} \frac{[B]}{EC_{50jB}|A=0} + Max_{Aj} \frac{[A]}{EC_{50jA}|B=0} + Max_{ABj} \frac{[A][B]}{EC_{50jA}|B=0 EC_{50jB}|A \rightarrow \infty}}{1 + \frac{[B]}{EC_{50jB}|A=0} + \frac{[A]}{EC_{50jA}|B=0} + \frac{[A][B]}{EC_{50jA}|B=0 EC_{50jB}|A \rightarrow \infty}}$$

Where,

$Basal_j$ is the response in the absence of A and B for the j th outcome

Max_{Aj} is the response to saturating concentrations of A in the absence of B for the j th outcome

Max_{Bj} is the response to saturating concentrations of B in the absence of A for the j th outcome

Max_{ABj} is the response in the presence of saturating concentrations of both ligands for the j th outcome

$EC_{50jA}|B=0$ is the EC₅₀ of A in the absence of B for the j th outcome

$EC_{50jB}|A=0$ is the EC₅₀ of B in the absence of A for the j th outcome

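### The SAP makes one non-linear model with 14 mean parameters the only joint analysis of Ang II and Ang(1-7), and pre-specifies no simpler model if it cannot be fitted

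*SAP*

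**What the plan says.** **Protocol 10.3.1.** Ang(1-7) and the Ang II/Ang(1-7) ratio "will both be modelled as per the primary analysis described above". The secondary row of the table adds: "A model including both Ang II and Ang(1-7) as co-predictors of RV function may also be built". The text below the table is firmer. It ranks the joint effect of the two peptides as an important secondary analysis, commits to developing a model that combines them because ACE2 is expected to change both, and foresees that several models may be tried.

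**SAP 2.1.** On the ratio: "However, the statistical model fitting will not take place". The reason given is that a participant with both peptides at 10 pg/mL and one with both at 10000 pg/mL have the same ratio but lie at different places on the response curves. The joint model "will now be the sole approach to modelling Ang II / Ang(1-7) ratios". No other departure from the protocol analysis is declared.

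**SAP 7.2.5 and 7.2.5.2.** The joint model is a Bayesian non-linear surface fitted to PASP and RV size ratio. Its output, Table 5.7, is conditional. If it cannot be fitted: "If data do not permit the planned model to be fitted no further modelling is proposed". The introduction to 7.2.5 adds that in such a case "simpler alternative models may not be attempted". Both statements go on to say that any alternative actually used would be described in the CSR. For convergence trouble, 7.2.5.2 offers a multivariate normal prior on the same parameters.

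**What stands apart from the joint model.** SAP 7.2.5.1: "The first supportive model will include Ang(1-7) as a time-point-level covariate instead of Ang II". That model's output, Table 5.5, is not conditional. For the primary analysis, SAP 7.1.5.1 names a fallback: logistic-type modelling of derived RV dysfunction status.

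**The concern.** The protocol promised a ratio model and a model of both peptides together. The SAP folds both into one demanding model and makes that model conditional. The primary analysis has a named second choice; this one does not.

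At stake is the question the protocol itself poses: how the probability of RV dysfunction changes when Ang II falls and Ang(1-7) rises together. If the non-linear model fails, either nothing answers it or an alternative is chosen after the data have been seen.

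**Working it through.** **1. Parameter count.** For each outcome the SAP lists Basal, Max_A, Max_B, Max_AB and three EC50s, which is 7 (matching the 7 x 7 prior matrix in 7.2.5.2). Two outcomes give 7 x 2 = 14 mean parameters. The 2 x 2 covariance matrix adds 3 distinct elements, giving 17. A linear model in both log10 peptides has 3 x 2 = 6 mean parameters, 3 covariance elements and rho, which is 10. (SAP 7.1.5 counts four elements for the 2 x 2 matrix; on that count the totals are 18 and 11.)

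**2. What remains if the joint model fails.**

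| Output | Remains? | Predicts P(RV dysfunction) when both peptides change? |
|---|---|---|
| Ratio summary statistics (SAP 2.1) | yes | no |
| Figures 3.4 and 3.5, ratio with PASP and RV size ratio | yes | no |
| Table 5.1, RAS biomarker correlations (does not name the ratio) | yes | no |
| Ang II model (Table 5.4) and Ang(1-7) model (Table 5.5) | yes | no, one peptide at a time |
| Joint model (Table 5.7) | no | it was the only one |

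**3. Is failure plausible?** SAP 7.1.5 already allows for non-convergence of the simpler linear primary model and reports that an unstructured time covariance gave convergence problems in simulation. SAP 7.1.1 warns that early termination may leave too little information even to explore covariates.

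The 7-parameter surface was also fitted by least squares to simulated PASP data. From the documents: log(Ang II) with mean 2.78 and SD 1.74 (Protocol 12.5.4). Assumed: Ang(1-7) log-normal with geometric mean 2 pg/mL (borrowed from the SAP pre-dose reference value), log-SD 1.0 to 1.74, independent of Ang II; residual SD 7 mmHg; Basal 34, Max_A 46, Max_B 28, Max_AB 38 mmHg; EC50s 16, 2 and 4; independent observations. Unstable means non-convergence, near-singularity or runaway estimates.

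| Observations | Non-linear fit unstable |
|---|---|
| 25 | 81-91% |
| 50 | 66-82% |
| 75 (25 participants x 3 days) | 49-74% |
| 150 | 26-57% |
| 450 (150 participants x 3 days) | 4-20% |

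The linear model was estimable in every run. This is not the SAP's MCMC, and the rates are indicative only.

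**4. The priors.** Each EC50 has an independent normal prior centred on zero with no positivity constraint. The prior probability of at least one negative EC50 is 1 - 0.5^3 = 87.5% per outcome and 1 - 0.5^6 = 98.4% over both outcomes. A negative EC50 lets the denominator of the mean function reach zero. The alternative prior is also centred on zero and does not bound the EC50s.

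**5. Does a linear model meet the SAP's objection to the ratio?** Take mu = alpha + gamma_A*log10(Ang II) + gamma_B*log10(Ang(1-7)). The 10/10 and 10000/10000 participants differ by 3*(gamma_A + gamma_B), so they are separated unless the slopes are exactly equal and opposite. That special case is the log-ratio model. In general

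gamma_A*L_A + gamma_B*L_B = [(gamma_A - gamma_B)/2]*(L_A - L_B) + [(gamma_A + gamma_B)/2]*(L_A + L_B),

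so (gamma_A - gamma_B)/2 is the slope on the log-ratio at a fixed overall level.

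**6. Precision for the planned contrast.** Between the SAP 7.1.5 reference points (Ang II 30, Ang(1-7) 2) and (8, 30), under the step 3 assumptions, the linear SE for mean PASP is approximately

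7*sqrt{[(ln 3.75/1.74)^2 + (ln 15/s_B)^2]/n}.

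At n = 75 with s_B = 1.0 this is 7*sqrt[(0.577 + 7.333)/75] = 2.3 mmHg; with s_B = 1.74 it is 7*sqrt[(0.577 + 2.422)/75] = 1.4 mmHg. The matching information-based SEs for the non-linear surface are 4.6 and 3.0 mmHg, about twice as wide.

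**7. Single-peptide versus adjusted slopes.** With illustrative standardised adjusted slopes of +0.4 (Ang II) and -0.3 (Ang(1-7)), the single-peptide slopes are 0.4 - 0.3r and -0.3 + 0.4r. At r = 0.5 they are +0.25 and -0.10; at r = -0.5 they are +0.55 and -0.50. The documents give neither the size nor the sign of r.

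**The case against.** A reader might infer that there is no fallback of any kind. The documents do not say that: a second prior structure is written down, and alternative models are allowed and would be reported. What stands is narrower. The second prior keeps the same 14 mean parameters, and the alternatives are neither named nor promised.

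A reader might also infer that no ratio result would be reported. That is wrong too. Summaries and plots stay, Table 5.1 probably covers the ratio, and the Ang(1-7) half of the same secondary objective keeps its full model.

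It is tempting to say that the single-peptide slopes are distorted and would hide a protective Ang(1-7) association. The objective is association, and a single-peptide slope validly estimates the marginal one. Step 7 shows that it may be smaller or larger than the adjusted slope. Since ACE2 lowers Ang II while forming Ang(1-7), a negative correlation is quite possible.

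Poor precision of individual EC50s would not settle the matter either. The planned output is predicted probabilities, and step 6 shows a contrast about twice as wide, not an absent one.

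Finally, the linear model has constant slopes and cannot describe the saturation and interaction that led the SAP to the non-linear form. That is a reason to keep both models. The setting is also modest, since SAP 2.4 states: "No formal statistical hypotheses are being tested in this exploratory study". The change to the ratio analysis is disclosed and reasoned.

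**Conclusion.** The point holds in limited form. The only committed joint analysis is conditional, and no simpler joint model is pre-specified. The ratio objective and the protocol's two-peptide analysis can therefore end without a pre-specified model-based estimate. The structural facts (14 mean parameters, conditional output, no named simpler model) come straight from the documents and need no assumption.

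How likely failure is cannot be fixed from the documents. Any rate depends on the final number of participants, which is not stated, and on assumed values for the Ang(1-7) distribution, the peptide correlation and the curve parameters. A reader might take the simulated rates as showing that the model will fail; they show only that failure is a realistic possibility at small numbers. The gap concerns a secondary objective of an exploratory study and does not touch the primary analysis. It is worth closing because the remedy is cheap.

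**What to change.** In SAP 7.2.5.2, pre-specify the following model, to be reported whether or not the non-linear model converges:

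mu_itj = alpha_j + gamma_Aj*log10(Ang II_it) + gamma_Bj*log10(Ang(1-7)_it),

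with the primary model's Sigma x AR(1) covariance and priors. Report, with 95% credible intervals:

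- both slopes for each outcome;
- the log-ratio contrast (gamma_A - gamma_B)/2;
- predicted P(RV dysfunction), and its differences, at the SAP 7.1.5 reference values, including the move from (30, 2) to (8, 30).

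Keep the non-linear model as the conditional analysis of saturation and interaction. Amend two statements to match: the one in SAP 2.1 that leaves the joint model as the only modelling route, and the one in 7.2.5.2 that limits reporting to the inference model. The cross-reference in SAP 2.1 should point to 7.2.5.2, where the joint model is described, not 7.2.5.1.

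**Cost.** SAP wording, one more run of code close to the primary model's, and one more secondary output. If the peptides are collinear, the separate slopes widen: the SE inflates by 1/sqrt(1 - r^2), which is 1.15 at r = 0.5 and 1.40 at r = 0.7. The linear model does not describe saturation or interaction.

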$EC_{50jB}|A \rightarrow \infty$ is the EC₅₀ of B in the presence of saturating concentrations of A for the j th outcome

[A] is time matched concentration of AngII (to aid review $[A_{it}]$ notation not used)

[B] is time matched concentration of Ang(1-7) (to aid review $[B_{it}]$ notation not used)

Also note that $EC_{50jA|B=0} \times EC_{50jB|A \rightarrow \infty} = EC_{50jB|A=0} \times EC_{50jA|B \rightarrow \infty}$, so the equation is symmetrical in A & B.

The vcov structure for $\Sigma_{(6 \times 6)}$ is constructed using the same approach as the primary analysis model but with an Identity matrix used for Tigma by first intent

$$\Sigma = \text{Sigma} \otimes \text{Tigma} =$$

$$\begin{pmatrix} \sigma_{y_1}^2 & \sigma_{y_1 y_2} \\ \sigma_{y_1 y_2} & \sigma_{y_2}^2 \end{pmatrix} \otimes \begin{pmatrix} 1 & 0 & 0 \\ 0 & 1 & 0 \\ 0 & 0 & 1 \end{pmatrix} \text{ and}$$

$$Var \begin{pmatrix} y_{t11} \\ y_{t21} \\ y_{t31} \\ y_{t12} \\ y_{t22} \\ y_{t32} \end{pmatrix} = \begin{pmatrix} \sigma_{y_1}^2 & 0 & 0 \\ 0 & \sigma_{y_1}^2 & 0 \\ 0 & 0 & \sigma_{y_1}^2 \\ \sigma_{y_1 y_2}^2 & 0 & 0 \\ 0 & \sigma_{y_1 y_2}^2 & 0 \\ 0 & 0 & \sigma_{y_2}^2 \end{pmatrix} \begin{pmatrix} \sigma_{y_1 y_2}^2 & 0 & 0 \\ 0 & \sigma_{y_1 y_2}^2 & 0 \\ 0 & 0 & \sigma_{y_1 y_2}^2 \end{pmatrix} \begin{pmatrix} \sigma_{y_2}^2 & 0 & 0 \\ 0 & \sigma_{y_2}^2 & 0 \\ 0 & 0 & \sigma_{y_2}^2 \end{pmatrix}$$

Uninformative prior distributions are assigned for the parameters as follows:

- Model parameters Basal_j, Max_{Aj}, Max_{Bj}, Max_{ABj}, EC_{50jA|B=0}, EC_{50jB|A=0} and EC_{50jB|A → ∞} (for j=1 (PASP) and 2 (RV Size ratio)) will each be assigned a prior of Normal(Mean=0, Var=1^E6). Note: By first intent these are all independent prior statements and correlation structures between related parameters would be expected to be observed in the observed posterior covariances of the model parameters (see Sensitivity analyses sections for alternative prior structures if model convergence issues are encountered).
- Σ , defined as the inverse of Sigma , is assigned an uninformative Wishart prior distribution: $\Sigma \sim \text{Wishart}(R, df)$ where: $R = \begin{pmatrix} 0.01 & 0 \\ 0 & 0.01 \end{pmatrix}$ and $df = 3$.
-

Model Checking & Diagnostics

- As per Primary analysis

Model Results Presentation

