- Once the model parameters have been estimated analogous predictions of the Posterior Probability of RV dysfunction (and differences between pre and post dose AngII levels) would be obtained as per Primary analysis. However, twice the number of items would be produced because there would be a need to condition on the two “pre and post dose” values for Ang(1-7) for each set of Ang II values.

Subgroup Analyses

- Not planned

Sensitivity and Supportive Analyses

- If model convergence issues are encountered the prior structure may be modified to group related sets of parameters together using a MVN (multivariate normal distribution). Two MVN priors distributions may be set up (one for each j) using parameters Basal_j , Max_{Aj} , Max_{Bj} , Max_{ABj} , $\text{EC}_{50jA|B=0}$, $\text{EC}_{50jB|A=0}$ and $\text{EC}_{50jB|A \rightarrow \infty}$. The MVN mean would be a vector of zeros and the prior for the vcov matrix of the model parameters would be an inverse-wishart with $R=Identity(7 \times 7)$ and $df=7$.
- An AR(1) structure may be attempted for the Σ vcov matrix and would use an uninformative uniform prior distribution over $-1, 1$ interval for parameter ρ

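### The joint Ang II / Ang(1-7) model leaves its EC50s unbounded and centred on zero, and its priors are not uninformative for the planned RV-dysfunction output

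*SAP*

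**What the plan says.** SAP 7.2.5.2 gives each outcome a mean function with seven structural parameters: a basal response, three plateaus (MaxA, MaxB, MaxAB) and three EC50s. The concentrations are divided by the EC50s.

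- **Main prior.** The list opens "Uninformative prior distributions are assigned for the parameters as follows". All seven parameters, for both outcomes, "will each be assigned a prior of Normal(Mean=0, Var=1^E6", stated as independent.
- **Fallback.** If convergence fails, the seven parameters of each outcome may share a multivariate normal prior. "The MVN mean would be a vector of zeros", and "the prior for the vcov matrix of the model parameters would be an inverse-wishart with" a 7 × 7 identity scale matrix and 7 degrees of freedom.
- **Bounds.** Neither specification states a truncation, a lower bound or a log parameterisation for the EC50s.
- **Output.** The model is to yield "analogous predictions of the Posterior Probability of RV dysfunction (and differences between pre and post dose AngII levels", at each of the two Ang(1-7) reference values.
- **If it cannot be fitted.** "If data do not permit the planned model to be fitted no further modelling is proposed". Alternatives are optional: SAP 7.2.5 says that "simpler alternative models may not be attempted", and 7.2.5.2 adds "However, if alternative model(s) are attempted and successful, they would be described in the CSR".

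SAP 2.1 drops the separate ratio model and leaves this joint model as the only way the ratio is addressed by modelling. Protocol 10.3.1 gives the joint effect prominence among the secondary analyses.

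**The concern.** A negative EC50 has no pharmacological meaning. If all three EC50s are positive, the denominator of the mean function is at least 1 at every concentration. If any one is negative, the denominator passes through zero at some positive concentration. The fallback cannot cure this, because it is unbounded and zero-centred too.

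The second problem is scale. The main prior uses one variance for a pressure near 38 mmHg, a ratio near 0.6 and concentrations in pg/mL. The fallback uses one identity matrix for the same mix of units, which ties the EC50 prior to the unit of the outcome. A prior that is flat for each parameter can still be strongly informative for a non-linear function of them, and the planned output is such a function. What is at stake is a secondary result that could show almost no difference because of the prior, with an interval too narrow to reveal it.

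**Working it through.** The plan states no prior mass or operating characteristics for this model, so there is no figure of its own to reproduce. As a check on the output function, the protocol's planning inputs (12.5.4) and reference values of 55.4 and 7.1 pg/mL gave differences of 34.1, 14.9, 22.8, 26.7, 22.6 and 13.4 points. Protocol Table 1b gives 33.9, 14.9, 22.5, 26.9, 22.5 and 13.2.

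**1. Sign of the EC50s (exact).** Main prior: 0.5 × 0.5 × 0.5 = 12.5% per outcome, and 0.125² = 1.56% for both outcomes. This does not depend on the variance. Fallback: a zero-mean normal with an inverse-Wishart(I, 7) covariance in 7 dimensions integrates to a spherical multivariate t with 7 − 7 + 1 = 1 degree of freedom, so the marginal figure is again 12.5% (direct draws: 12.6%).

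**2. Location of the EC50 prior.** References are from SAP 7.1.5: Ang II 30 and 8 pg/mL, Ang(1-7) 2 and 30 pg/mL. With SD 1000, P(8 < EC50 < 30) = 0.9% for Ang II and P(2 < EC50 < 30) = 1.1% for each Ang(1-7) EC50. In the fallback, given four response parameters with sum of squares q, each EC50 is t with 5 df and scale √((1+q)/5):

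- Response parameters at 38 mmHg: q = 4 × 38² = 5776, scale 34.0 pg/mL.
- Response parameters at 0.61: q = 4 × 0.61² = 1.49, scale 0.71 pg/mL. The 95% range is ±1.8 pg/mL, below both Ang II references.

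**3. Zeros in the plausible range.** For Ang II up to 92.1 pg/mL (protocol 12.5.1) and Ang(1-7) up to 30, the denominator reaches zero or below, per outcome, in 5.5% of main-prior draws with variance 1E6, 87% if the printed 1^E6 is taken literally as 1, and 86% under the fallback.

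**4. Prior for the planned output.** The thresholds are those of SAP 7.1.5 (40 mmHg, 0.6), with residual SDs 8 and 0.15 and correlation 0.5 from protocol 12.5.4. At Ang(1-7) = 2, moving Ang II from 30 to 8 under the main prior gives an absolute difference of 15 points or less in 96.8% of draws, and a difference of at least 30 points in 1.5%. Restricting the EC50s to positive values leaves the first figure at 97.4%.

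**5. Illustrative posterior.** The SAP mean function, identity time structure and Wishart prior were fitted to 40 simulated datasets per setting. Assumed: 25 or 50 participants; three independent visits; protocol means and SDs; correlation r of both outcomes with log Ang II of 0.3 or 0.6; Ang(1-7) log-normal with geometric mean 4 and log-SD 1.2, independent of Ang II (the documents give no distribution); true EC50s log-uniform on 5–80 (Ang II) and 2–30 (Ang(1-7)); one response shape. The alternative prior uses log EC50 centred at ln 16.1 (Ang II) and ln 7.75 (Ang(1-7)) with SD 2, and Basal/Max N(38, 16²) and N(0.61, 0.30²).

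Mean posterior median of the difference in points [95% interval coverage], Ang(1-7) = 2:

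| r, participants (truth) | SAP main | Main, EC50s truncated at zero | SAP fallback | Log EC50 and outcome-scale Basal/Max |
|---|---|---|---|---|
| 0.3, 25 (13.7) | 2.8 [18%] | 3.1 [18%] | 4.4 [42%] | 8.8 [92%] |
| 0.3, 50 (13.6) | 4.0 [22%] | 4.2 [28%] | 8.5 [75%] | 11.3 [95%] |
| 0.6, 25 (31.7) | 25.4 [88%] | – | 28.0 [95%] | 29.2 [100%] |
| 0.6, 50 (31.9) | 30.3 [92%] | – | 30.9 [90%] | 31.2 [98%] |

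The Monte Carlo standard error of coverage is up to √(0.25/40), about 8 points.

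- **Ang(1-7) = 30, r = 0.3** (truths 11.2 and 11.8 at 25 and 50 participants): main 2.2 [45%] and 3.4 [42%]; alternative 6.6 [92%] and 8.2 [95%].
- **Which change matters** (r = 0.3, 50 participants, Ang(1-7) = 2): log EC50 alone 3.8 [30%]; rescaled Basal/Max alone 6.3 [58%]; both 11.3 [95%].
- **Posterior mass on at least one negative EC50**, averaged over datasets: 69–81% under the main prior and 25–72% under the fallback.

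A separately written sampler under the same assumptions (16 datasets per setting) gave, at r = 0.3 with 25 and 50 participants, 2.9 and 3.7 points against truths of 13.7 and 13.5, with 19% and 31% coverage. The alternative prior gave 9.1 and 10.3 points with 88% coverage.

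**The case against.** - **The 12.5% is not what does the damage.** This stands: truncating at zero moves the estimate by only 0.2–0.3 points at r = 0.3. It is a reason to change the scales as well as the sign.
- **With variance 1E6 few prior draws have a zero in the plausible range.** True (5.5%), though under the fallback the share is 86%.
- **The posterior figures rest on assumptions.** The shape, the Ang(1-7) distribution and the EC50 ranges are not in the documents. The alternative prior is also favoured: 7.75 is √(2 × 30), the centre of the assumed Ang(1-7) EC50 range, and Basal/Max are centred on the simulated means. Centred off the truth, it still gave 8.4 [80%] and 10.8 [90%] at r = 0.3. A cruder approximation (importance sampling, known residual covariance, outcomes fitted separately, 10–12 datasets) found milder shrinkage at 50 participants, 8.2 against 13.8 with 6 of 10 intervals covering, but some of its datasets had low effective sample size. The full sampler was reproduced; the exact sizes remain illustrative.
- **Some fits had not converged and would not be reported.** The maximum R-hat under the SAP priors was 2.7, and SAP 7.1.5 asks for at least three chains. The median was 1.00–1.01, in the repeat as well, so poor mixing does not explain the shrinkage.
- **The SAP may already cover this.** SAP 7.1.5 allows responses to be rescaled, but for the primary model, and that moves neither the zero centre nor the EC50 sign. SAP 7.1.5.1 defers model checking to an internal guide that is not available here, so a prior sensitivity check cannot be ruled out; none is written in the SAP.
- **The consequence is small.** The study ended early, no formal hypothesis is tested, and Table 5.7 is conditional. This stands, and it limits the severity. Fewer data, however, give the prior more weight.

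**Conclusion.** The point holds. The absence of any positivity constraint is plain from the text of both specifications, and the 12.5% is exact. The uninformative label, which applies to the main prior list, does not hold for the planned output: before any data that prior puts about 97% of its mass on an absolute difference of 15 points or less.

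Under the stated assumptions, a moderate association (r = 0.3) is pulled most of the way to zero by the main prior, with coverage near 20%. The fallback is less severe at 50 participants (8.5 of 13.6 points, 75%). With a strong association (r = 0.6) the effect is small at 50 participants for Ang(1-7) = 2. The prior arithmetic is certain. The direction of the posterior effect at r = 0.3 is well supported, while its size depends on one response shape, independent visits and an assumed Ang(1-7) distribution. The primary Ang II analysis and the single-peptide models are not affected.

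**What to change.** In SAP 7.2.5.2, for both the main and the fallback specification:

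1. Parameterise every EC50 on the log scale, with centre and spread justified from the assay range. Truncation at zero is the minimum for the sign problem, but does not by itself correct the output.
2. Set the Basal and Max priors on each outcome's own scale. In the illustrative runs neither this nor the log scale alone restored coverage; the two together did.
3. In the fallback, scale the response and EC50 blocks separately instead of using one identity matrix.
4. Add a prior sensitivity check, including a prior-predictive check, for the difference in probability of RV dysfunction.
5. Correct 1^E6 to 1E6, as printed for the primary model in SAP 7.1.5, wherever that variance is kept.

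The cost is a few lines of SAP text and code. No data collection or design change is needed.
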